#### **Multiplicity adjustment between age groups:**

A hierarchical sequential hypothesis testing (fixed-sequence method) will be used to adjust multiplicity to preserve the family-wise Type I error rate ( $\alpha = 0.05$ ), starting with the oldest age group, followed by the middle age group, and then followed by the youngest age group. The primary series immunogenicity coprimary endpoint hypotheses for the oldest age group (6 years to  $< 12$  years of age) will be tested first at  $\alpha$  level of 0.05 in Part 1 expansion or Part 2. If the testing in the oldest age group in Part 2 is statistically significant (meeting the noninferiority success criteria of the coprimary endpoints), the  $\alpha$  level of 0.05 will be passed to the testing of the primary series coprimary endpoint hypotheses in the middle age group (2 years to  $< 6$  years of age) in Part 2. If the testing in the middle age group is statistically significant at  $\alpha$  level of 0.05, then the  $\alpha$  0.05 is preserved for testing the primary series coprimary endpoint hypotheses in the youngest age group (6 months to  $< 2$  years of age) in Part 2.

#### **6.4.3. Secondary Analysis of Antibody-Mediated Immunogenicity Endpoints**

For each group, the following evaluations will be performed at each time point at which blood samples are collected for immunogenicity (unless otherwise specified).

- GM level of anti-SARS-CoV-2-specific bAb with corresponding 95% CI will be provided at each time point. The 95% CIs will be calculated based on the t-distribution of the log-transformed values then back transformed to the original scale for presentation. The following descriptive statistics will be also provided at each time point: the number of subjects (n), median, minimum and maximum.
- GM fold-rise (GMFR) of SARS-CoV-2-specific bAb levels with corresponding 95% CI will be provided at each post-baseline timepoint over pre-injection baseline at Day 1. The 95% CIs will be calculated based on the t-distribution of the log-transformed values then back transformed to the original scale for presentation. The following descriptive statistics will be also provided at each time point: the number of subjects (n), median, minimum and maximum.

Proportion of subjects with fold-rise  $\geq 2$ , and fold-rise  $\geq 4$  of serum SARS-CoV-2 specific bAb levels from Visit Day 1 (baseline) at each post injection time points will be tabulated with 2-sided 95% Clopper Pearson CIs

- GMT of SARS-CoV-2-specific nAb values with corresponding 95% CI will be provided at each time point using the same method mentioned above.
- GMFR of SARS-CoV-2-specific nAb values with corresponding 95% CI will be provided at each post-baseline timepoint over pre-injection baseline at Day 1 using the same method mentioned above.

Proportion of subjects with fold-rise  $\geq 2$ , and fold-rise  $\geq 4$  of serum nAb from Visit Day 1 (baseline) at each post-injection time points will be tabulated with 2-sided 95% Clopper-Pearson CIs.

- Proportion of subjects with seroresponse due to vaccination will be tabulated with 2-sided 95% Clopper-Pearson CIs at each post-baseline timepoint. The definition of seroresponse can be found in [Section 3.1](#).
- Per the study protocol, if the visit for the second dose (Day 29) is disrupted and cannot be completed at Day 29 (+7 days) as a result of the COVID-19 pandemic (self-quarantine or disruption of clinical site activities following business continuity plans and/or local government mandates for “stay at home” or “shelter in place”), the window may be extended to Day 29 + 21 days. More rigid visit window will be used in the Per-Protocol Immunogenicity Subset, -7/+14 for Day 29 visit, as appropriate.

## 6.5. Efficacy Analysis

Efficacy analyses will be performed using the FAS, mITT, mITT1 and PP Set for Efficacy. The mITT1 Set will be the primary analysis set used for efficacy analysis of efficacy endpoints starting from 14 days after first dose, and PP Set for Efficacy will be the primary analysis set used in the efficacy analyses for efficacy endpoints starting 14 days after second dose, unless otherwise specified. Subjects will be included in the treatment group to which they were randomized.

**Baseline SARS-CoV-2 status** is described in [Section 6.1](#). Baseline SARS-CoV-2 status, the serology test results at baseline, the RT-PCR test results at baseline will be summarized by age group and treatment group.

Participants with baseline positive or missing SARS-CoV-2 status will be excluded from the PP Set for Efficacy Analysis.

In this study, the serology test results and the RT-PCR test results will be summarized by visit.

### 6.5.1. Endpoint Definition/Derivation

#### 6.5.1.1. Derivation of SARS-CoV-2 Infection

This is a secondary efficacy endpoint, which is a combination of COVID-19 and asymptomatic SARS-CoV-2 infection for participants with negative SARS-CoV-2 status at baseline: the incidence of SARS-CoV-2 infection counted starting 14 days after the second dose of IP will be summarized by treatment group. SARS-CoV-2 infection will be defined in participants with negative SARS-CoV-2 at baseline:

- bAb level against SARS-CoV-2 nucleocapsid protein negative (as measured by *Roche Elecsys*) at Day 1 that becomes positive (as measured by *Roche Elecsys*) post-baseline, OR
- Positive RT-PCR post-baseline.

Derivation of this secondary efficacy endpoint is summarized in Table 3 below.

**Table 3. Derivation for SARS-CoV-2 Infection**

| Baseline SARS-CoV-2 Status | Post-baseline assessments |  | Endpoint: SARS-CoV-2 infection |
|-----------------------------------|----------------------------------|--|---------------------------------------|
|                                   | PCR test post baseline           | bAb levels against SARS-CoV-2 Nucleocapsid |                                       |
|                                   |                                  |  |                                       |

|                      |   |      |
|----------------------|---|------|
| Negative at Baseline | Positive (either at nasal swab test, or at symptom-prompt nasal swab test)     | Case |
| Negative at Baseline | Positive (at Post baseline visit or later) as measured by Roche Elecsys | Case |

The date of documented infection will be the earlier of:

- Date of positive post-baseline RT-PCR result, or
- Date of positive serology test result based on bAb specific to SARS-CoV-2 nucleocapsid

The time to the first SARS-CoV-2 infection will be calculated as:

Time to the 1st SARS-CoV-2 infection = Date of the 1st documented infection – Date of randomization + 1. (For Part 1, switch date of randomization to date of 1st injection)

Cases will be counted starting 14 days after the second injection, i.e. date of documented infection – Date of the 2nd injection  $\geq$  14.

SARS-CoV-2 infection cases will also be summarized based on tests performed at least 14 days after first dose.

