### 3.2. Secondary Endpoints

The secondary objective will be evaluated by the following endpoints:

- The GM values of SARS-CoV-2 S protein-specific bAb on Day 1, Day 57 (1 month after Dose 2), Day 209 (6 months after Dose 2), Day 394 (1 year after Dose 2), BD-Day 1 (at least 3 months or 6 months after Dose 2), BD-Day 29 (1 month after mRNA-1273 booster dose or third dose), BD-Day 181 (6 months after mRNA-1273 booster dose or third dose), and BD-Day 366 (1 year after mRNA-1273 booster dose or third dose).
- The GM values of SARS-CoV-2-specific nAb on Day 1, Day 57 (1 month after Dose 2), Day 209 (6 months after Dose 2), Day 394 (1 year after Dose 2), BD-Day 1 (at least 3 months or 6 months after Dose 2), BD-Day 29 (1 month after mRNA-1273 booster dose or third dose), BD-Day 181 (6 months after mRNA-1273 booster dose or third dose), and BD-Day 366 (1 year after mRNA-1273 booster dose or third dose).
- The incidence of SARS-CoV-2 infection including symptomatic and asymptomatic infection (by serology and/or RT-PCR), starting 14 days after the second dose of IP, and starting 14 days after the first dose of IP. SARS-CoV-2 infection will be defined in participants with negative SARS-CoV-2 at baseline:
  - bAb level against SARS-CoV-2 nucleocapsid protein negative at Day 1 that becomes positive (as measured by Roche Elecsys) post baseline, OR
  - Positive RT-PCR post baseline.
- The incidence of SARS-CoV-2 infection measured by RT-PCR and/or bAb levels against SARS-CoV-2 nucleocapsid protein (by Roche Elecsys) post baseline in participants with negative SARS-CoV-2 at baseline, in the absence of any COVID19 symptoms, starting 14 days after the second dose of IP, and starting 14 days after the first dose of IP

- The incidence of the first occurrence of CDC Case Definition of COVID-19 post baseline, starting 14 days after the second dose of IP, and starting 14 days after the first dose of IP. COVID-19 is defined as symptomatic disease based on the following criteria according to CDC case definition:
  - The participant must have a positive test for SARS-CoV-2 by RT-PCR; AND
  - Either

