**Table 1: Planned Age Groups and mRNA-1273 Dose Levels in Part 1 and Part 2, and Part 3 of the Study**

| Age Group             | Part 1                        |                     |                     | Part 2  |                              | mRNA-1273
25 µg
2 doses of
primary
series +a third
dose
(Month 0, 1,
5) |
|-----------------------|-------------------------------|---------------------|---------------------|---|------------------------------|--|
|                       | mRNA-1273
25 µg            | mRNA-1273
50 µg  | mRNA-1273
100 µg | Selected Dose
Level of mRNA-1273 From Part 1 | Placebo                      |  |
| 6 years to < 12 years |                               | Study Arm 1 (n=375) | Study Arm 2 (n=375) | Study Arm 8 (n=3,000)                           | Study Arm 9 (n=1,000)        | Study Arm 14 (n= approximately 300)  |
| 2 years to < 6 years  | Study Arm 7 (Optional) (n=75) | Study Arm 3 (n=75)  | Study Arm 4 (n=75)  | Study Arm 10 (n=up to 3,000)                    | Study Arm 11 (n=up to 1,000) |  |
| 6 months to < 2 years | Study Arm 5 (n=150)           | Study Arm 6 (n=150) |                     | Study Arm 12 (n=up to 3,000)                    | Study Arm 13 (n=up to 1,000) |  |

Note: mRNA = messenger RNA.

1. Four months post-Dose 2  $\pm$  28 days (at least 3 months and up to 5 months after Dose 2)

The study will begin with the oldest age group (6 years to < 12 years) and age de-escalate. Each age group will begin with Part 1 and may advance to Part 2 and Part 3 independently. The mRNA-1273 investigational vaccine or placebo will be administered as 2 intramuscular (IM) injections, approximately 28 days apart for Part 1 and Part 2. For Part 3, the mRNA-1273 investigational vaccine will be administered as 3 IM injections approximately 28 days apart for the 2 doses of primary series followed by a third dose at least 3 months and up to 5 months after receipt of the second dose of the primary series. The mRNA-1273 dose levels that will be evaluated in each age group in Part 1, Part 2 and Part 3 of the study are given in Table 1.

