#### **6.5.1.2. Derivation of Asymptomatic SARS-CoV-2 Infection**

This is a secondary efficacy endpoint: the incidence of asymptomatic SARS-CoV-2 infection measured by RT-PCR and/or serology tests obtained post-baseline visits counted starting 14 days after the second injection in participants with negative SARS-CoV-2 status at baseline.

Asymptomatic SARS-CoV-2 infection is identified by absence of symptoms and infections as detected by RT-PCR or serology tests. Specifically:

- Absent of COVID-19 symptoms
- AND at least one from below:
  - bAb level against SARS-CoV-2 nucleocapsid protein negative (as measured by Roche Elecsys) at Day 1 that becomes positive (as measured by Roche Elecsys) post-baseline, OR

- Positive RT-PCR test post-baseline (at scheduled or unscheduled/illness visits)

The date of documented asymptomatic infection is the earlier date of positive serology test result based on bAb specific to SARS-CoV-2 nucleocapsid due to infection, or positive RT-PCR at scheduled visits, with absence of symptoms.

The time to the asymptomatic SARS-CoV-2 infection will be calculated as:

Time to the asymptomatic SARS-CoV-2 infection = Date of asymptomatic SARS-CoV-2 infection test – Date of randomization + 1. (For Part 1, switch date of randomization to date of first injection)

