**Table 1. Derivation for SARS-CoV-2 Infection**

| Baseline SARS-CoV-2 Status | Post-baseline assessments  |   | Endpoint: SARS-CoV-2 infection |
|-----------------------------------|---|---|---------------------------------------|
|                                   | PCR test post baseline  | bAb levels against SARS-CoV-2 Nucleocapsid                                    |                                       |
| Negative at Baseline of each part | Positive (either at nasal swab test, or at symptom-prompt nasal swab test) |   | Case                                  |
| Negative at Baseline of each part |   | Positive (at post-baseline visits) as measured by Roche Elecsys | Case                                  |

The date of documented infection will be the earlier of:

- Date of positive post-baseline RT-PCR result, or
- Date of positive serology test result based on bAb specific to SARS-CoV-2 nucleocapsid

In long-term analysis (including Part 2 Open-Label Phase), SARS-CoV-2 infection cases will be counted starting 14 days after the second injection of mRNA-1273, i.e. date of documented infection - date of the 2nd injection  $\geq$  14. SARS-CoV-2 infection cases will also be summarized based on tests performed at least 14 days after first dose of IP.

In booster dose analysis, SARS-CoV-2 infection cases will be counted starting 14 days after the booster dose of mRNA-1273, i.e. date of documented infection - date of the booster injection  $\geq$  14.

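### Serology-only infections are dated by the first positive sample, so Day 57 and BD-Day 29 seroconversions count as infections at least 14 days after the dose even when acquired earlier

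*SAP*

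**What the plan says.** The document holds two plans: one for Part 1 and the Part 2 blinded phase (the main SAP), and one for the Part 2 open-label phase, boosters and Part 3 (the booster SAP).

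- **Case definition.** In main SAP section 3.2 the serological route to a case is "bAb level against SARS-CoV-2 nucleocapsid protein negative at Day 1 that becomes positive (as measured by Roche Elecsys) post baseline". The only negative required is the one at Day 1. Section 6.5.1.1 repeats this.
- **Date.** "The date of documented infection will be the earlier of" two dates: that of a positive RT-PCR and, in the SAP's words, "Date of positive serology test result based on bAb specific to SARS-CoV-2 nucleocapsid". A case with no PCR result therefore takes the date of the blood sample.
- **Counting rule.** "Cases will be counted starting 14 days after the second injection, i.e. date of documented infection" minus the date of the second injection must be at least 14 days.
- **Asymptomatic infection.** Section 6.5.1.2 dates by test in the same way, with cases "counted starting 14 days after the second injection in participants with negative SARS-CoV-2 status at baseline".
- **Booster.** The text after Table 1 of the booster SAP reads: "In booster dose analysis, SARS-CoV-2 infection cases will be counted starting 14 days after the booster dose of mRNA-1273". The same text repeats the Dose 2 rule for the long-term analysis.

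Neither plan has a rule for back-dating, interval censoring or a fresh negative after the dose. The PP Set for Efficacy (section 5.3), the main set for the post-Dose 2 endpoints, asks for negative tests at baseline only.

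**The concern.** The endpoint is labelled as infection from 14 days after Dose 2, but a seroconversion shows only that infection happened somewhere between the last negative and the first positive sample. In Part 1 and in Part 2 Cohorts B and C that interval runs from Day 1 to Day 57, so it covers the time before Dose 2 and the two weeks after it.

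Case status then depends on how an infection was found as well as on when it occurred. A child infected on Day 10 and PCR-positive that day is dated Day 10 and not counted. A child infected on the same day, never PCR-positive and first seropositive at Day 57, is counted. Silent infections are the most exposed, because no symptom prompts a swab, and they are the subject of the asymptomatic endpoint. What is at stake is whether two secondary endpoints measure what their label says.

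**Working it through.** The SAP gives no expected number of events for these endpoints, so there is no figure to reproduce. The check is one of timing.

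**Inputs from the SAP**
- Doses are "administered as 2 intramuscular (IM) injections, approximately 28 days apart for Part 1 and Part 2" (section 4.1), so Dose 2 falls on Day 29 and the window opens on Day 29 + 14 = Day 43.
- Part 1 nucleocapsid serology: Days 1, 57, 209 and 394 (section 6.4.1).
- Part 2 blood draws (Table 2): Cohort A on Days 1, 29 and 57; B on Days 1, 57 and 209; C on Days 1, 57 and 394; 176 children in each. Cohort D has no Day 57 draw.
- RT-PCR swab before dosing on Day 29 (Appendix E).
- Analysis window for the Day 57 sample: Days 44 to 133 (Table 5).
- Booster draws: Appendix G of the booster SAP.

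**Assumptions not in the SAP:** the shape of the infection hazard, the lag from infection to seropositivity, and how far back the Day 29 swab detects infection. Each is varied below.

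**Formula.** Share before the window = (infection time from last negative to Day 43) / (infection time from last negative to the positive sample). Days caught by the swab come off both terms. A lag shortens the end of the denominator.

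| Scenario | Calculation | Share before window |
|---|---|---|
| Part 1, Cohorts B/C: constant hazard, no lag, no swab capture | 42/56 | 75% |
| Swab catches previous 7 days | 35/49 | 71% |
| Swab catches previous 14 days | 28/42 | 67% |
| Swab catches previous 28 days | 14/28 | 50% |
| Lag 7 days, no swab capture | 42/49 | 86% |
| Lag 14 days | 42/42 | 100% |
| Cohort A, Day 29 blood nucleocapsid-tested and negative, no lag | 14/28 | 50% |
| Cohorts A-C pooled, no lag, no swab capture | (14+42+42)/(28+56+56) = 98/140 | 70% |
| Hazard doubling every 14 days, no lag | (2^3-1)/(2^4-1) = 7/15 | 47% |
| Hazard halving every 14 days, no lag | (1-1/8)/(1-1/16) | 93% |
| Day 57 sample drawn on Day 133 | 42/132 | 32% |

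**Booster.** The booster is given on BD-Day 1, so the window opens on BD-Day 15. A first positive at BD-Day 29 has 14/28 = 50% of its exposure before the window. At BD-Day 181 the share is 14/180 = 8%, and at BD-Day 366 it is 14/365 = 4%.

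**Later samples.** A first positive at Day 209 or 394 after a negative Day 57 lies wholly inside the window for any lag up to 14 days.

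**Reach.** In Part 2, 3 x 176 = 528 of up to 4,000 children per age group (13%) have a Day 57 draw. In Part 1 the Day 57 draw is scheduled in Arms 3 to 7 and for about 75 children in each of Arms 1 and 2; it is optional for the other 300 in each of those two arms.

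**The case against.** The strongest case on the other side is about reach and consequence.

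- **Reach.** The percentages are shares of Day 57 seroconversions. The endpoint also includes RT-PCR positives and later seroconversions, and most Part 2 children have no Day 57 blood. A reader might infer that three quarters of the endpoint's cases are misplaced. The SAP gives no case mix, so that does not follow. This limit stands.
- **Rate.** A reader might infer that the reported incidence rate is inflated. Section 6.5.2 runs person-time from randomization (first injection in Part 1), so the earlier days are already in the denominator. Under a constant hazard, Day 1-57 seroconversions over Day 1-57 person-time do not overstate the rate. Inflation is not shown. The number and percentage of children with an event, which section 6.5.2 also reports, still carry the wrong label.
- **Vaccine-placebo contrast.** A reader might infer a biased efficacy estimate. If protection is weaker before Day 43, a side-by-side reading of Day 57 seroconversions would indeed be diluted. But section 6.5.2 plans incidence by group with exact Poisson intervals and no ratio, efficacy estimate or test; efficacy is inferred through immunobridging. Booster incidence is exploratory and has no placebo group.
- **Other counts.** Cases are also summarized from 14 days after Dose 1 and, as a sensitivity analysis, from randomization or first injection. These answer other questions and leave the post-Dose 2 count as it is.
- **Openness.** The SAP calls the date one of documented infection, so dating by test is disclosed. The label of the endpoint is not qualified to match.

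**Conclusion.** The point holds as a defect of derivation in two secondary endpoints. By the SAP's own rules, an on-schedule Day 57 seroconversion with no earlier PCR date always counts as a post-Dose 2 + 14 day case, whenever the infection occurred. That part needs no assumption.

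The size does. The share of exposure before the window is 75% in the base case for Part 1 and Cohorts B and C, and 50-71% if the Day 29 swab catches the previous 28 to 7 days. It is 50% in Cohort A if the Day 29 blood is nucleocapsid-tested, and higher with any seroconversion lag. It can fall below half with steeply rising incidence or a late draw. For BD-Day 29 it is 50%. The defect should be corrected, but it does not touch the RT-PCR-based COVID-19 endpoints or the immunobridging, and the documents do not support a claim that the rate or an efficacy estimate is biased by a stated amount.

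**What to change.** In sections 6.5.1.1 and 6.5.1.2 of both SAPs:

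1. Do not count a serology-only case first positive at Day 57 (or BD-Day 29) with no PCR date in the post-Dose 2 (post-booster) + 14 day endpoint. Tabulate these cases by group on a separate line as infections of undetermined timing, interval-censored between last negative and first positive sample. Keep them in the from-randomization and post-Dose 1 counts.
2. Count a serology-only case at Day 209 or 394 when the Day 57 sample was negative, and state what happens when Day 57 is missing.
3. Keep first positives at BD-Day 181 or 366 in the booster analysis, labelled as test-dated. A blanket demand for a negative at least 14 days after the booster would remove nearly all booster serology-only cases: no group in Appendix G has BD-Day 29 and a later draw, and only sub-Cohort E has even an optional BD-Day 15 draw. For these samples only 8% or 4% of the exposure precedes the window.
4. Make the person-time of the restricted count match its numerator. Dropping cases while still counting time from randomization would lower the rate artificially.

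PCR-dated cases do not change. The cost is SAP wording and a derivation change using data already collected. The downside is fewer serology-only cases in the post-Dose 2 + 14 day count, and none from Cohort A, which has no draw after Day 57. The 14 of 56 days (25%) behind a Day 57 case in Cohorts B and C that do fall inside the window also move to the separate line.

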#### **6.5.1.2. Derivation of Asymptomatic SARS-CoV-2 Infection**

This is a secondary efficacy endpoint: the incidence of asymptomatic SARS-CoV-2 infection measured by RT-PCR and/or serology tests obtained post-baseline visits counted starting 14 days after the second injection in participants with negative SARS-CoV-2 status at baseline.

Asymptomatic SARS-CoV-2 infection is identified by absence of symptoms and infections as detected by RT-PCR or serology tests. Specifically:

- Absent of COVID-19 symptoms
- AND at least one from below:
  - bAb level against SARS-CoV-2 nucleocapsid protein negative (as measured by Roche Elecsys) at Day 1 that becomes positive (as measured by Roche Elecsys) post-baseline, OR

- Positive RT-PCR test post-baseline (at scheduled or unscheduled/illness visits)

The date of documented asymptomatic infection is the earlier date of positive serology test result based on bAb specific to SARS-CoV-2 nucleocapsid due to infection, or positive RT-PCR at scheduled visits, with absence of symptoms.

The time to the asymptomatic SARS-CoV-2 infection will be calculated as:

Time to the asymptomatic SARS-CoV-2 infection = Date of asymptomatic SARS-CoV-2 infection test – Date of randomization + 1. (For Part 1, switch date of randomization to date of first injection)

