### **6.5.2. Analysis Method**

The number and percentage of subjects who had an event (i.e. the first asymptomatic SARS-CoV-2 infection) will be summarized in the PP set for Efficacy.

The incidence rate will be provided by age and vaccination group, calculated as the number of cases divided by the total person-time. The 95% CI of the incidence rate will be calculated using the exact method (Poisson distribution) and adjusted by person-time.

Person-time is defined in Part 2 as the total time from randomization date to the date of event, last date of study participation, censoring time, or efficacy data cutoff date, whichever is earlier. For Part 1, switch randomization date to date of first injection.

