**Table 5 . Visit Window**

| Visit                             | Target Study Day              | Visit Window in Study Day |
|-----------------------------------|-------------------------------|---------------------------|
| Nasal Swabs for SARS-CoV-2 |                               |                           |
| Day 1                             | 1 (Date of First Injection)   | 1, Pre-first-dose         |
| Day 29 (Month 1)                  | 29 (Date of Second Injection) | [2, 43]                   |

|                                  |                             |  |
|----------------------------------|-----------------------------|--|
| Day 57 (Month 2)                 | 57                          | [44,133]   |
| Day 209 (Month 7)                | 209                         | [134, 301]                                       |
| Day 394 (Month 13)               | 394                         | $\geq 302$                                       |
| Immunogenicity            |                             |  |
| Part 1                           |                             |  |
| Day 1                            | 1 (Date of First Injection) | 1, Pre-first-dose                                |
| Day 57 (Month 2)                 | 57                          | [44,133]   |
| Day 209 (Month 7)                | 209                         | [134, 301]                                       |
| Day 394 (Month 13)               | 394                         | $\geq 302$                                       |
| Part 2 where Day 29 is selected  |                             |  |
| Day 1                            | 1 (Date of First Injection) | 1, Pre-first-dose and prior to the randomization |
| Day 29                           | 29                          | [2,43], Pre-second-dose                          |
| Day 57                           | 57                          | [44,133]   |
| Part 2 where Day 209 is selected |                             |  |
| Day 1                            | 1 (Date of First Injection) | 1, Pre-first-dose and prior to the randomization |
| Day 57                           | 57                          | [44,133]   |
| Day 209                          | 209                         | [134,301]  |
| Part 2 where Day 394 is selected |                             |  |
| Day 1                            | 1 (Date of First Injection) | 1, Pre-first-dose and prior to the randomization |

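### An unscheduled positive RT-PCR can establish an asymptomatic infection but cannot date it, so such a case has no clear date or a late one

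*SAP*

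**What the plan says.** The file holds two SAPs, one for Part 1 and the Part 2 blinded phase, the other for the Part 2 open-label phase, boosters and Part 3. The same mismatch stands in section 6.5.1.2 of both.

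- **Case definition (6.5.1.2, both SAPs).** COVID-19 symptoms must be absent, and one of two tests must be positive. One is conversion to positive nucleocapsid serology. The other is "Positive RT-PCR test post-baseline (at scheduled or unscheduled/illness visits").
- **Date rule (next paragraph, both SAPs).** "The date of documented asymptomatic infection is the earlier date of positive serology test result", or a "positive RT-PCR at scheduled visits, with absence of symptoms".
- **Time to event (6.5.1.2, blinded-phase SAP only).** "Time to the asymptomatic SARS-CoV-2 infection = Date of asymptomatic SARS-CoV-2 infection test", counted from randomization.
- **Counting rule (6.5.1.2, blinded-phase SAP).** Cases are "counted starting 14 days after the second injection in participants with negative SARS-CoV-2 status at baseline".
- **Person-time (6.5.2, blinded-phase SAP).** "Person-time is defined in Part 2 as the total time from randomization date to the date of event" or another end point, whichever is earlier. Section 6.5.2 of the open-label/booster SAP also ends person-time at the event date.
- **Overall infection (6.5.1.1, under Table 3).** The documented date is the earlier of two dates, the first being "Date of positive post-baseline RT-PCR result, or" and the second the positive serology date. No type of visit is excluded.

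**The concern.** The definition admits a source of evidence that the date rule leaves out. The event date decides whether a case falls at least 14 days after the dose and where its person-time stops, so a case without a date cannot be processed as the plan requires. A case dated by a later test carries the wrong date.

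Section 6.5.1.1 describes overall infection as combining COVID-19 with asymptomatic infection. Every counted asymptomatic case should then also be a counted infection. With different date rules for the component and the composite, that need not hold.

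**Working it through.** The plan states no figure to reproduce. The check sets the rules side by side and uses the scheduled days for scale.

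**1. Which tests make a case and which can date it**

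| Positive result, no symptoms | Makes a case (6.5.1.2) | Dates asymptomatic infection (6.5.1.2) | Dates overall infection (6.5.1.1) |
|---|---|---|---|
| Nucleocapsid serology | yes | yes | yes |
| PCR, scheduled visit | yes | yes | yes |
| PCR, unscheduled or illness visit | yes | **no** | yes |

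Only the third row is inconsistent. Neither SAP gives a fallback date for it. The time-to-event formula refers to an infection test without saying which. If it means the documented date defined just above it, the gap remains. If it means any qualifying test, the section holds two date rules.

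**2. Effect at the 14-day cut-off**

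Take dose 2 on Day 29, a symptom-free positive unscheduled PCR on Day 35 and positive serology on Day 57 (Cohorts A to C all have Day 57 blood). The rule is event date minus dose 2 date ≥ 14, so the cut-off is Day 29 + 14 = Day 43.

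- Overall infection: dated Day 35; 35 − 29 = 6, below 14, not counted.
- Asymptomatic infection: dated Day 57; 57 − 29 = 28, counted.

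The child is in the component but not in the composite. A positive scheduled swab on Day 57 would do the same without serology. The PP Set for Efficacy (5.3) requires negative status only at baseline, so it does not remove this child on that ground. The contradiction concerns the count from dose 2. In the count from 14 days after dose 1, Day 35 already qualifies (35 − 1 = 34).

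**3. Delay after Day 57**

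Scheduled swabs (Table 5 and Appendix E, blinded-phase SAP) fall on Days 1, 29, 57, 209 and 394, with Day 43 added at the selected cell-mediated-immunity sites. After Day 57 the gaps are 209 − 57 = 152 days and 394 − 209 = 185 days. After an mRNA-1273 booster, swabs fall on BD-Day 29 and BD-Day 181, again 152 days apart. Infections in these intervals are already past the cut-off, so the delay changes person-time.

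Serology follows a different timetable. Table 2 gives, for Part 2:

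- Cohort A: nothing after Day 57.
- Cohort B: Day 57, then Day 209 (152 days).
- Cohort C: Day 57, then Day 394 (394 − 57 = 337 days).
- Cohort D: only a stored biomarker sample around Day 30.
- Cohort E: Days 43, 209 and 394.

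If an age group enrols its full 4,000, Cohorts A to C hold 3 × 176 = 528 and Cohort E holds 24. Cohort D then holds 4,000 − 528 − 24 = 3,448, or 86%. For these children serology offers almost no route to a date. If the only positive is an unscheduled PCR and later swabs are negative, no date is available.

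**4. Scale of the person-time effect**

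A late case adds at most 185 days to the denominator through the swab route. Assume that all 1,000 placebo recipients of an age group contribute at least 57 days: 1,000 × 57 = 57,000 person-days, and 185 / 57,000 = 0.3%. For 3,000 vaccine recipients, 3,000 × 57 = 171,000, and 185 / 171,000 = 0.1%. Longer follow-up makes both smaller. Per case this is slight; adding or losing a case in the numerator matters more.

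**The case against.** Four objections carry weight.

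- **The formula may supply a date.** Its wording could be read as the date of the qualifying test, including an unscheduled PCR. This stands in part: in the blinded-phase SAP the case is ambiguous rather than impossible to date. It does not cure the date rule, and section 6.5.1.2 of the open-label/booster SAP has no such formula.
- **Few children are affected.** Section 6.5.1.3 arranges illness visits for children who report symptoms from the CDC list, and one symptom from that broad list is enough. A PCR-positive child at such a visit will usually be a COVID-19 case. Other unscheduled visits arise from reactogenicity or adverse events. This stands: the group is residual.
- **The infection is not lost.** Section 6.5.1.1 dates any positive post-baseline PCR, so the overall endpoint still records the infection, subject to its own 14-day rule. This stands too.
- **Little depends on the endpoint.** It is summarised by incidence rates with exact Poisson intervals and no hypothesis test, and section 6.5 of the open-label/booster SAP treats it as exploratory.

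A reader might infer that undated cases are dropped. The SAPs do not say so; they give no rule for a case without a date, so dropping it or assigning a date ad hoc are both only possibilities. A reader might also infer that delays of 152 to 185 days carry cases across the 14-day cut-off. They do not: those gaps begin at Day 57, after the cut-off has passed. The shift across the cut-off runs from before Day 43 to Day 57 and is a matter of weeks.

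**Conclusion.** The inconsistency is real and stands in the current text of both SAPs. An unscheduled or illness-visit PCR can establish an asymptomatic infection but is not a permitted source of its documented date. This has three consequences:

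- a case with no other positive has no date under that rule and may be dropped or dated ad hoc;
- a case from before the cut-off can be re-dated to Day 57 and counted as asymptomatic infection while the composite excludes it;
- a case after Day 57 can gain up to 152 or 185 days of person-time through the swab route, with serology timing that differs by cohort.

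These statements assume on-time visits, dose 2 on Day 29, and a later date that still falls within the analysis period. The documents do not give the number of cases affected, which is probably small. A reader might infer a material bias in the incidence rates or a threat to the primary conclusions; the documents support neither. This is a minor defect in a secondary, untested endpoint, worth correcting because two programmers could follow the text and obtain different results.

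**What to change.** In section 6.5.1.2 of both SAPs, define the documented date as the earliest qualifying positive test: the earlier of positive anti-nucleocapsid serology or any positive post-baseline RT-PCR (scheduled, unscheduled or illness visit), with symptoms absent. State that this same date is used in the 14-day rule and person-time, and in the time-to-event formula of the blinded-phase SAP. This brings the component into line with section 6.5.1.1.

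If the limit to scheduled visits was intended, the alternative is to restrict the PCR part of the case definition to scheduled visits. That also makes the endpoint programmable, but it gives up cases the plan now accepts and leaves the date rules of component and composite different.

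The cost is one phrase in each date rule and a sentence linking the date to its uses. No new data, sample size or alpha change is needed. If outputs have already been produced, affected cases can be found by listing symptom-free participants with a positive off-schedule RT-PCR and comparing their dates under sections 6.5.1.1 and 6.5.1.2.
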